10.7 Analysis of Exploratory Endpoints

Exploratory endpoints will be assessed as follows:

- Proportion of subjects who develop dose-limiting symptoms to approximately 2000 mg cumulative baked egg protein at screening and subsequently tolerate approximately 2000 mg cumulative baked egg protein with no more than mild symptoms at study exit
- Proportion of subjects who tolerate a single highest dose of 2000 mg dried egg white protein with no more than mild symptoms at the exit DBPCFC
- Maximum dose of dried egg white protein reached with no more than mild symptoms during the exit DBPCFC
- Change from baseline in the single highest tolerated dose of dried egg white protein at the exit DBPCFC
- Use of epinephrine as rescue medication at the exit DBPCFC compared with use at the screening DBPCFC
- Change from baseline in egg white-specific and egg white component serum immunoglobulins
- Change from baseline in mean wheal diameter on SPT to egg white
- Change from baseline in ACT/C-ACT, EASI, and TNSS scores
- Change from baseline in FAQLQ and FAIM scores

Full details for these analyses will be provided in the statistical analysis plan.

11 STUDY COMMITTEES AND COMMUNICATIONS

An independent, external DSMC will be established to monitor the study for safety. The committee will meet on a periodic basis to review the study safety data in accordance with the DSMC charter.

12 LABORATORY REQUIREMENTS

12.1 Clinical Laboratory Tests

Clinical laboratory tests (hematology, immunology) will be performed according to the schedules of activities ([Appendix 4](#), [Appendix 5](#)). Samples will be stored until the specified analyses are completed and then will be destroyed in accordance with standard laboratory practice and applicable local regulations, unless consent is obtained for longer storage.

A list of the required clinical laboratory tests and other evaluations is provided in [Table 18](#). All samples for laboratory analysis must be collected, prepared, labeled, and shipped according to laboratory requirements.

All clinical laboratory tests will be performed by the central laboratory specified in Form FDA 1572 Section 4 unless otherwise specified. The central laboratory reference ranges will be used. A local clinical laboratory may be used to assess samples at unscheduled visits or urgent care to evaluate an adverse event. Central laboratory samples should also be obtained whenever possible during unscheduled visits. No local laboratory data will be entered into the study database and local laboratories will not be included on Form FDA 1572.

Additional details are provided in the laboratory manual.

Table 18: Clinical Laboratory Tests

Hematology	Immunology	Other
Red blood cell count Hemoglobin Hematocrit Platelet count	Total immunoglobulin (Ig) E Egg white-specific and egg white component IgE	Pregnancy test (serum at screening; urine thereafter) for all females of childbearing potential
White blood cell count with differential (percent and absolute) 
• Total neutrophils• Lymphocytes• Monocytes• Eosinophils• Basophils	Egg white-specific IgG4	

12.2 Optional Blood Samples for Potential Future Substudies

Optional blood samples will be collected at certain study sites according to the schedules of activities ([Appendix 4](#), [Appendix 5](#)) and stored for potential future studies in patients with food allergy and/or patients receiving egg OIT.

13 INVESTIGATOR AND ADMINISTRATIVE REQUIREMENTS

The sponsor must confirm that a study site is activated before an investigator enrolls subjects in the study, and the following documents must be available:

- Fully executed and signed Form FDA 1572
- Fully executed clinical trial agreement
- Current curriculum vitae from the investigator (also applies to all subinvestigators listed on the Form FDA 1572)
- Financial disclosure by the investigator (also applies to all subinvestigators listed on the Form FDA 1572)
- Investigator-signed protocol signature page
- Investigator-signed acknowledgment of receipt of the current investigator brochure
- EC and regulatory authority approval letter
- EC-approved informed consent and assent forms
- Additional documents as necessary per local requirements

If an investigator changes during the course of the study, the sponsor and any local regulatory authorities, as applicable, must first approve the change of investigator and the new investigator must provide the sponsor all of the relevant documents listed above.

The sponsor personnel or representatives may visit the study site, if necessary, before initiation of the study to review information with study site personnel about protocol requirements pertaining to the study treatment, case report forms, monitoring, serious adverse event reporting, and other relevant information.

13.1 Ethics

13.1.1 Ethics Committee

Before initiating the study, the investigator or sponsor will obtain confirmation from the EC that the EC is properly constituted and compliant with all requirements and local regulations.

The investigator or sponsor will provide the EC with all appropriate material, such as the protocol, current investigator brochure, site-specific informed consent form, assent form (where required), and other written information provided to the subjects. The study will not be initiated until the appropriate EC and regulatory authority approval is obtained in writing for all required documentation, and copies are received by the sponsor.

EC and regulatory authority approval will be obtained for any substantial protocol amendments and informed consent/assent revisions before implementing the changes. The investigator or sponsor will provide appropriate reports on the progress of the study to the EC, per local requirements, and to the sponsor or designee in accordance with applicable local regulations.

13.1.2 Ethical Conduct of the Study

This study will be conducted under the guiding principles of the World Medical Association Declaration of Helsinki, including current Good Clinical Practice (GCP) according to ICH guidelines, and national regulations as appropriate. The study will be conducted under a protocol reviewed and approved by an EC and applicable regulatory authorities; the study will be conducted by scientifically and medically qualified persons; the anticipated benefits of the study are in proportion to the risks; the rights and welfare of the subjects will be respected; the physicians conducting the study do not find the hazards to outweigh the potential benefits; and written informed consent and assent (where required) will be obtained for each subject before any protocol-specific tests or evaluations are performed.

13.1.3 Subject Information and Informed Consent and Assent

A properly executed, written informed consent, in compliance with the Declaration of Helsinki, ICH GCP, US Code of Federal Regulations (CFR) for Protection of Human Subjects (21 CFR 50.25[a,b,c], CFR 50.27, and CFR Part 56, Subpart A), local regulations, and relevant national regulations as appropriate will be obtained from each subject or pediatric subject's parent/caregiver before entering the subject in this study. A properly executed age-appropriate assent form will also be obtained from each pediatric subject where required and as appropriate per local requirements. Where required by local authorities, both parents must sign the consent form before a child can be enrolled in the study. The sponsor will prepare the informed consent and assent forms for submission to the EC. The EC must approve the document before the investigator implements it.

The investigator will provide a copy of the signed informed consent form to each subject or signed informed consent and assent form to a subject's parent/caregiver, and will maintain the original documents within the subject's clinical record per local requirements. The investigator will also fully document the informed consent process in the subject's source documents.

Informed consent and assent procedures may be affected by a pandemic, epidemic, or other emergency not related to the study as described in [Appendix 3](#).

13.1.4 Maintaining Subject Confidentiality

All reports and subject samples will be identified only by the subject ID number and year of birth to maintain subject confidentiality. Additional subject confidentiality issues are addressed in the clinical trial agreement, in the informed consent form signed by the parent/legal guardian, and in the study participant's assent form (where required).

13.2 Data Quality Assurance

13.2.1 Data Management

Clinical data management will be performed by the sponsor or designee according to procedures described in a comprehensive data management plan. The data management plan will include procedures for processing the data from this study, and will describe the responsibilities of the sponsor and designee when clinical data management is provided by an external vendor. The data management plan will include a list of the standard operating procedures that apply to this study.

Adverse events and medications will be coded using MedDRA and the WHO-DD, respectively. The dictionary versions will be named in the data management plan.

13.2.2 Case Report Forms

The study will use an electronic data capture system, and a guide will be provided for completing case report forms. All case report forms are to be fully completed, reviewed, and signed by the investigator or subinvestigators listed on the Form FDA 1572 or other appropriate local regulatory authority documents.

13.2.3 Study Monitoring

The sponsor or designee will monitor this study in accordance with current GCP guidelines. By signing this protocol, the investigator grants permission to the sponsor or designee and appropriate regulatory authorities to conduct onsite monitoring of all appropriate study documentation. To ensure the accuracy of data collected on the case report forms, it is mandatory that sponsor representatives (eg, study monitor) have direct access to original source documents (eg, paper or electronic subject records, subject charts, and laboratory reports) needed to verify the entries on case report forms. During the review of these documents, the anonymity of the subject will be respected with strict adherence to professional standards of confidentiality.

A study monitor will contact and visit the site regularly and will be allowed, on request at a mutually acceptable time, to inspect the various original medical records/source documents (paper or electronic) related to the study. The study monitor will be responsible for inspecting the case report forms at regular intervals throughout the study, to verify the adherence to the protocol and the completeness and correctness of all case report form entries. The investigator agrees to cooperate with the study monitor to ensure that any problems detected during these monitoring visits are resolved.

Study monitoring may be affected by a pandemic, epidemic, or other emergency not related to the study as described in [Appendix 3](#).

13.2.4 Study Audits

During the study and after study completion, it is likely that one or more quality assurance audits will be conducted by the sponsor or authorized representatives, or both. The purpose of the audit is to ensure that the study is (or was) conducted and monitored in compliance with the protocol as well as recognized GCP guidelines and regulations. These audits will also increase the likelihood that the study data and all other study documentation can withstand a regulatory authority inspection. If such audits are to occur, they will be arranged for a reasonable and agreed upon time.

13.3 Investigational Product Accountability

The investigator must maintain accurate records of all investigational product supplies received. All records must be made available to the sponsor, authorized representatives, and appropriate regulatory agencies, upon request.

Current ICH GCP guidelines and local and national regulations require the investigator to ensure that investigational product deliveries from the sponsor are received by a responsible person (eg, pharmacist), and the following:

- That such deliveries are recorded, for example, on the sponsor's investigational product accountability log or other sponsor-approved pharmacy log
- That investigational product is handled and stored safely and properly in accordance with the label and the study protocol
- That investigational product is only administered or dispensed to study subjects in accordance with the protocol
- That any used or unused investigational product is returned by the subject at each required visit
- That any unused investigational product is returned to the sponsor-designated facility or standard procedures for the alternative disposition of unused investigational product are followed and only after approval by the sponsor representative
- A detailed accounting of any investigational product accidentally or deliberately destroyed

Investigational product inventory and accountability records for the investigational products will be kept by the study site. Investigational product accountability throughout the study must be documented. The following guidelines are therefore pertinent:

- The investigator agrees not to supply investigational product to any persons except the subjects in this study.
- The investigator/pharmacist will keep the investigational products in a pharmacy or other locked and secure storage facility under controlled storage conditions as required by the investigational product label, accessible only to those authorized by the investigator to dispense these investigational products.

- The investigator/pharmacist will maintain an investigational product inventory. The inventory will include details of materials received and a clear record of when they were dispensed and to which subject.
- The investigator/pharmacist agrees to conduct a final investigational product supply inventory and to record the results of this inventory on the investigational product accountability record at the conclusion or termination of this study. It must be possible to reconcile delivery records with those of used and returned investigational product. Any discrepancies must be accounted for. Appropriate forms of deliveries and returns must be signed by the person responsible.

Used or unused investigational product may be destroyed at the study site according to standard institutional procedures if the sponsor agrees with the procedure, and after investigational product accountability has been conducted by the sponsor or representative, unless otherwise approved. A copy of the standard institutional procedure for destroying investigational products will be provided to the sponsor or designee upon request for review and approval before the first onsite destruction. Unused investigational product not destroyed at the site must be returned to the sponsor-designated facility at the end of the study or upon expiration.

13.4 Retention of Records

The investigator must make original study data (paper or electronic) accessible to the study monitor, other authorized sponsor representatives, and regulatory agency inspectors upon request. A file for each subject must be maintained that includes the signed informed consent and assent forms and copies of all source documentation related to that subject. The investigator must ensure the reliability and availability of source documents from which the information on the case report form was derived.

Investigators must maintain all study documentation for at least 2 years following the approval of the investigational product, or until 2 years after the investigational product program is discontinued, or longer if required by local regulations. Study documentation includes but is not limited to all essential documents as defined in ICH E6 Guidelines for Good Clinical Practice. The sponsor or designee will notify the investigator when any records may be discarded, but investigators must comply with local and national regulations.

13.5 Protocol Deviations

The investigators and study site staff will conduct the study in accordance with the approved protocol. Any intentional or unintentional change, divergence, or departure from the study design or procedures will be considered a protocol deviation. Protocol deviations will be documented in accordance with the study manual and may include electronic data capture or other means.

Where necessary, the investigator may deviate from the protocol to eliminate an immediate hazard to a study subject, although every effort should be made to discuss this with the sponsor medical monitor in advance.

13.6 Study Termination

The sponsor will end this study following completion of the study objectives, or earlier if deemed necessary.

The sponsor reserves the right to terminate the study anytime and for any reason. When the sponsor is aware of information on matters concerning the quality, efficacy, and safety of the investigational products, as well as other important information that may affect proper conduct of the clinical study, the sponsor may terminate the study and send a written notice of the termination along with the reasons to the investigator and EC/regulatory authorities as required.

In the event of early study closure for reasons other than safety or quality, subjects who complete at least 9 months of study treatment, including at least 4 weeks at 300 mg/day, may have the exit DBPCFC and open baked whole egg food challenge and complete the study. Subjects must tolerate the 300 mg daily dose of study product for approximately 2 consecutive weeks before having the exit DBPCFC. Subjects who do not complete at least 9 months of study treatment, including at least 4 weeks at 300 mg/day, will discontinue early from the study.

If an investigator or the investigator's EC intends to terminate participation in the study, the investigator must immediately inform the sponsor and provide the reason for it.

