Up-dosing will be approximately 6 months (22-40 weeks), with dose escalation occurring approximately every 2 weeks. Daily doses of study product during up-dosing will be 1, 3, 6, 12, 20, 40, 80, 120, 160, 200, 240, and 300 mg/day. The first dose of study product at each new dose level will be administered under medical supervision at the study site; the remaining doses at each dose level will be administered daily at home as tolerated. Dose adjustments may be allowed. Subjects who reach the 300 mg/day dose within 40 weeks and tolerate the first 300 mg dose with no more than mild symptoms that are not dose-limiting will begin the maintenance period. Subjects who do not reach the 300 mg/day dose within 40 weeks of day 1 will discontinue early from the study.

Subjects who begin maintenance treatment will continue daily dosing with study product at 300 mg/day for approximately 12 weeks, which may be extended by up to an additional 4 weeks to accommodate dose adjustments during the last 2 weeks of maintenance. Study site visits will occur approximately every 4 weeks. Study product will be administered under medical supervision at the study site during maintenance visits; subsequent maintenance doses will be administered daily at home as tolerated. At the end of maintenance, subjects will have an exit DBPCFC up to a single highest challenge dose of 2000 mg dried egg white protein (4043 mg cumulative) or placebo, followed by an open baked whole egg food challenge within 14 days after the second day of the exit DBPCFC. Subjects must tolerate the 300 mg daily dose of study product for approximately 2 consecutive weeks before having the exit DBPCFC.

Subjects who complete the exit DBPCFC and attempt the open baked whole egg food challenge will exit (complete) the study. Study treatment assignment will be unblinded for a subject after study exit and after all major data queries for the subject are resolved. For a subject who discontinues early from the study, study treatment assignment will be unblinded after the study is completed. Eligible subjects will have the option to enroll in an open-label, follow-on study to receive AR201 treatment until it becomes commercially available or product development is terminated.

At early discontinuation or study exit, subjects with unresolved adverse events or who had gastrointestinal (GI) adverse events of interest (ie, GI adverse events that result in dose

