5.2.3.2 Up-Dosing Procedures

Up-dosing procedures are listed in the schedule of activities in [Appendix 5](#). Additional procedures will be performed at the 80 mg and 300 mg up-dosing visits ([Appendix 5](#)).

Up-dosing study site visits are every 2 weeks for approximately 6 months (minimum 22 weeks if up-dosing proceeds without holding or reducing a dose level; maximum 40 weeks).

Up-dosing will begin when subjects begin daily dosing with study product at 1 mg/day at home for 2 weeks. Subjects who tolerate 1 mg/day for 2 weeks will return to the study site to receive a 3 mg dose. Subjects who tolerate the 3 mg dose at the study site will receive study product to continue daily dosing at home with 3 mg/day for a total of 2 weeks. AR201 dose escalations will continue in this manner up to 300 mg/day as shown in [Table 3](#). Dose adjustments may be allowed ([Section 8.7.3.2](#), [Section 8.7.4](#)).

Subjects who reach the 300 mg/day dose within 40 weeks and tolerate the first 300 mg dose with no more than mild allergy symptoms that are not dose-limiting will begin maintenance treatment ([Section 5.2.3.3](#)). Subjects who do not reach the 300 mg/day dose within 40 weeks of day 1 will discontinue early from the study ([Section 5.3](#)).

Table 3: Up-Dosing Dose-Escalation Schedule (1-300 mg)

Dose Number	Study Product Dose (mg)	Interval (weeks)	Increase From Previous Repeated Dose
1	1	2	Not applicable
2	3	2	200%
3	6	2	100%
4	12	2	100%
5	20	2	67%
6	40	2	100%
7	80	2	100%
8	120	2	50%
9	160	2	33%
10	200	2	25%
11	240	2	20%
12	300	-	25%

Up-dosing begins with the first 1 mg/day dose of study product at home.

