5.2.3.3 Maintenance Procedures

The maintenance procedures are listed in [Appendix 5](#). Maintenance visits will occur every 4 weeks for approximately 12 weeks. Dose adjustments may be allowed ([Section 8.7.3.2](#), [Section 8.7.4](#)). The maintenance period may be extended by up to an additional 4 weeks to

accommodate dose adjustments during the last 2 weeks of maintenance. Study product will be administered under medical supervision at the study site during maintenance visits; subsequent maintenance doses will be administered daily at home as tolerated.

An exit DBPCFC will be performed at the end of maintenance, followed by an open baked whole egg food challenge within 14 days after the second day of the exit DBPCFC ([Section 9.1.1](#), [Section 9.1.2](#), [Appendix 1](#), [Appendix 2](#), [Appendix 5](#)). The 300 mg daily dose of study product must be tolerated for approximately 2 consecutive weeks before having the exit DBPCFC. In exceptional circumstances when the 300 mg daily dose is not taken for approximately 2 consecutive weeks before the planned exit DBPCFC for reasons unrelated to the study product, the medical monitor should be contacted to determine whether the exit DBPCFC is to be attempted. Discussion with the medical monitor is required to determine whether the exit DBPCFC and/or open baked whole egg food challenge may be attempted if the food challenge is delayed due to circumstances that create a safety risk (eg, an intercurrent illness).

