2.7 Study Exit

Subjects who complete study treatment (initial dose escalation, up-dosing, and maintenance, which may be extended when restrictions are in place) will continue blinded study treatment and have remote study visits every 4 weeks until regular study site visits resume. Study exit will not occur until regular study site visits resume. Study exit procedures will be conducted in accordance with the study protocol.

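### Section 13.6 sets a 9-month (39.1-week) floor for the exit challenge at early closure, but the protocol's own no-hold course lasts 34 weeks

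*Protocol*

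**What the plan says.** Section 13.6 opens its closure rule with "In the event of early study closure for reasons other than safety or quality". In that event, subjects with at least 9 months of study treatment, of which at least 4 weeks at 300 mg/day, may have the exit DBPCFC and the baked egg challenge. For everyone else it states: "Subjects who do not complete at least 9 months of study treatment, including at least 4 weeks at 300 mg/day, will discontinue early". It makes no exception for a subject who has already finished maintenance.

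The length of the course is set elsewhere:

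- Section 3.1: "Up-dosing will be approximately 6 months (22-40 weeks), with dose escalation occurring approximately every 2 weeks".
- Section 5.2.3.2 gives the range as "minimum 22 weeks if up-dosing proceeds without holding or reducing a dose level; maximum 40 weeks".
- Section 5.2.3.3: "Maintenance visits will occur every 4 weeks for approximately 12 weeks". An extension of up to 4 weeks is allowed, but only for dose adjustments in the last 2 weeks.

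In ordinary conduct the exit DBPCFC follows the end of maintenance, with no month count (Sections 3.1 and 5.2.3.3). Section 3.5 and the definition of early treatment discontinuation in Section 5.3 both treat 9 months as approximate. Appendix 3 Section 2.7 describes completion by treatment periods: "Subjects who complete study treatment (initial dose escalation, up-dosing, and maintenance, which may be extended when restrictions are in place"). Section 10.5.1 counts subjects who discontinue early before the exit DBPCFC as nonresponders.

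**The concern.** The closure rule uses a fixed calendar minimum that the protocol's own schedule does not reach. A subject who up-doses exactly as planned and completes all of maintenance has had less than 9 months of treatment. If the study closes before that subject's exit DBPCFC, Section 13.6 as worded requires early discontinuation, and Section 10.5.1 turns this into a primary-endpoint failure without any challenge having been done.

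The rule also orders subjects the wrong way round. Someone who needed about 35 weeks to reach 300 mg/day and has had only 4 weeks there may be challenged. Someone who reached 300 mg/day in 22 weeks and completed 12 weeks there may not.

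**Working it through.** **Inputs.** Dose steps: Section 5.2.3.2, Table 3. Maintenance: Section 5.2.3.3. Initial dose escalation: 2 days (Section 5.2.3.1). Visit window: 3 days either side (Section 5.2.1). Up-dosing limit: 40 weeks. Month length: 365.25 / 12 = 30.4375 days, with a 28-day month as the lenient alternative.

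**The protocol's own figure.** Table 3 has 11 two-week intervals (1 to 240 mg) before 300 mg: 11 × 2 = 22 weeks. This reproduces the stated minimum.

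**The threshold.**
- Calendar months: 9 × 30.4375 = 273.9 days; 273.9 / 7 = 39.1 weeks.
- 28-day months: 9 × 28 = 252 days = 36 weeks.

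**The no-hold course.** 22 + 12 = 34 weeks = 238 days. Adding the 2 initial dose-escalation days gives 240 days. Shortfall: 273.9 − 240 = 33.9 days, or 252 − 240 = 12 days with 28-day months.

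**Other full courses (up-dosing plus maintenance).**

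| Course | Weeks | Against 39.1 | Against 36 |
|---|---|---|---|
| 22 + 12 | 34 | 5.1 short | 2 short |
| 24 + 12 | 36 | 3.1 short | meets |
| 26 + 12 | 38 | 1.1 short | meets |
| 22 + 12 + 4 (full extension) | 38 | 1.1 short | meets |
| 6 calendar months (26.1) + 12 | 38.1 | 1.0 short | meets |

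**Break-even.** With 12 weeks of maintenance, the rule is met only from 39.1 − 12 = 27.1 weeks of up-dosing (36 − 12 = 24 weeks with 28-day months).

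**The slow up-doser.** With only 4 weeks at 300 mg/day, 39.1 − 4 = 35.1 weeks of up-dosing meets the rule. That is inside the 40-week limit.

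**Can visit windows close the gap?** There are 11 up-dosing visits (3 to 300 mg) and 3 maintenance visits, 14 in all. If lateness accumulates, the most it can add is 14 × 3 = 42 days. Closing 33.9 days needs 33.9 / 3 = 11.3, so 12 of the 14 visits each 3 days late. For the 6-month course, 182.6 + 84 + 2 = 268.6 days; the gap is 273.9 − 268.6 = 5.3 days, which two visits each 3 days late would cover.

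**The case against.** The strongest reply is that 9 months is a nominal label for the whole course. Sections 3.5 and 5.3 use it loosely, Section 13.6 repeats the Section 5.3 formula with one qualifier changed, and its evident purpose is generous: to let subjects with shortened maintenance still be challenged. That may well be what the sponsor meant. But Section 13.6 states a minimum and a mandatory consequence, and sites act on the text.

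The second reply is reach. Closure must be early and for a reason other than safety or quality, and the subject must have finished maintenance in under 9 months with the challenge still outstanding. The challenge follows the end of maintenance, and Appendix 1 has its two days scheduled within 7 days. This stands and limits the point, although Section 5.2.3.3 itself provides for the case "if the food challenge is delayed due to circumstances that create a safety risk (eg, an intercurrent illness"). Pandemic delay is not an aggravating case: under Appendix 3 Section 2.7 subjects who have completed treatment "will continue blinded study treatment and have remote study visits every 4 weeks until regular study site visits resume", so they accrue time toward 9 months.

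Third, 34 weeks is the shortest course, and for the nominal 6-month up-doser the gap is only about 5 days. That is correct, but it does not help the subject who follows the schedule without holds.

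Fourth, Section 10.2 defines a completer population, and Appendix 3 Section 5 allows a sensitivity analysis that excludes such subjects. Neither changes the primary ITT result, and the second is optional and sits in the pandemic guidance.

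Finally, the proposed wording still excludes a subject at week 33 with 11 weeks at 300 mg/day. That is true, so it does not remove every inequity between fast and slow up-dosers. That subject, however, has not finished the schedule; the defect here concerns those who have.

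**Conclusion.** The concern holds, and it is minor. No protocol figure is miscalculated; the fault is that the Section 13.6 floor and the scheduled course do not fit together. The shortfall for a no-hold course is 34 days with calendar months and 12 days with 28-day months, so the conclusion does not depend on how a month is counted. For courses with 24 or more weeks of up-dosing it does: they fall short only with calendar months.

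The consequence rests on reading Section 13.6 as written together with the nonresponder rule in Section 10.5.1. Ordinary conduct is unaffected. How many subjects would be caught depends on the closure date and cannot be derived from the protocol, so no direction or size of bias is claimed.

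**What to change.** Keep the 9-month floor and add completion of the schedule as an alternative.

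- Section 13.6, first sentence: after the 9-month and 4-week condition, insert *or who complete the scheduled up-dosing and maintenance periods, whichever comes first*.
- Section 13.6, final sentence of that paragraph: replace the repeated condition with *Subjects who meet neither condition discontinue early*.
- Section 5.3 definition: add *or the scheduled up-dosing and maintenance periods, whichever comes first*. This is largely a matter of consistency, since Section 5.3 is already approximate.

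The requirement of about 2 consecutive weeks at a tolerated 300 mg/day stays. Merely softening the Section 13.6 minimum to an approximate one would match Sections 3.5 and 5.3, but would leave it to judgement whether 34 weeks (7.8 calendar months) counts as about 9 months.

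With the change, a no-hold subject qualifies at week 34 instead of week 39.1. The cost is three sentences of wording and possibly a few more exit challenges at closure, all of them already part of the planned schedule.
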